### 4.2.1 Hematologic Dose Limiting Toxicity

Hematologic DLT is defined as follows:

- Grade 4 neutropenia lasting > 7 days
- $\geq$  Grade 3 febrile neutropenia lasting > 48 hours or any  $\geq$  Grade 3 febrile neutropenia associated with hemodynamic compromise or objective evidence of infection
- Grade 4 thrombocytopenia, irrespective of duration
- Grade 3 thrombocytopenia associated with clinically significant bleeding
- $\geq$  Grade 3 hemolysis

The following events will be specifically **excluded** from the definition of hematologic DLT:

- $\geq$  Grade 3 lymphopenia
- Grade 3 anemia that is not associated with other clinically significant complications

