In a non-GLP study, a higher repeat-dose level of 20 mg/kg/dose administered at a 2-week interval was associated with similar, but greater, clinical pathology MGC018-related changes that in some cases resulted in microscopic correlates. These included an inflammatory response (increased fibrinogen, CRP, and globulin concentrations and decreased albumin concentrations) that was likely associated with cutaneous skin lesions, suppressed hematopoiesis (decreased red cell mass and decreased reticulocyte, neutrophil, and platelet counts) that correlated with decreased hematopoietic cellularity of the sternal bone marrow, and decreased lymphocyte counts that correlated with lymphoid depletion of the thymus. Microscopic skin findings were more severe in animals administered the higher repeat-dose level of 20 mg/kg/dose. Skin erosion that consisted of separation of the epidermis from the underlying basement membrane and dermis resulted in grossly visible ulcers and led to euthanasia in extremis in 1 out of 3 animals.

Animals that received MGC018 as a single dose at  $\geq$  20 mg/kg and necropsied 48 hours post-dose had microscopic findings not observed at later necropsy days or in animals that received 10 mg/kg.

Based on the GLP toxicology study, the HNSTD for MGC018 was 10 mg/kg/dose administered as a 1-hour IV infusion Q3W (total of 3 doses) as there were no MGC018-related life-threatening toxicities, irreversible findings, or mortality. This corresponds to a peak and systemic exposure of 260.27 mcg/mL ( $C_{max}$ ) and 11821 hr\*mcg/mL [area under the concentration-time curve ( $AUC_{0-504hr}$ )] for the conjugated antibody, 233.85 mcg/mL ( $C_{max}$ ) and 11475 hr\*mcg/mL ( $AUC_{0-504hr}$ ) for the total antibody and 309.5 pg/mL ( $C_{max}$ ) and 11188 hr\*pg/mL ( $AUC_{0-504hr}$ ) for SYD986 (payload), respectively.

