## 4.2 Dose Limiting Toxicity

For the purposes of guiding study decisions regarding dose escalation, DLTs will be based on study drug-related AEs or laboratory abnormalities that occur up to Study Day 21 of Cycle 1 in the Dose Escalation Phase only for Module A and Study Day 42 of Cycle 1 in the Dose Escalation Phase only for Module B. The severity of AEs will be graded according to the National Cancer Institute Common Terminology Criteria for Adverse Events version 4.03 (NCI CTCAE v4.03). Dose-limiting toxicities will be defined separately for hematologic, non-hematologic, and hepatic non-hematologic events.

In general, for participants who experience toxicity that may meet the criteria for a DLT, subsequent administration of the study drugs should be held pending management and/or resolution of the event and assessment of attribution to the study drug. Criteria for discontinuation of therapy are outlined in [Section 5.4](#).

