#### **4.3 Dose Escalation Rules**

The Dose Escalation Phase of this trial will proceed using a conventional 3 + 3 + 3 approach.

If 0 of the first 3 participants treated at a given dose level experience a drug-related DLT during the DLT evaluation period, the dose will be escalated, and 3 participants will be enrolled and treated at the next higher dose level (up to the planned highest dose level).

If 1 of the first 3 participants treated at a given dose level experiences a drug-related DLT, then 3 additional participants will be enrolled at that dose level (thus making a total of 6 participants in this cohort) to further assess the safety of MGC018 alone (Module A) or in combination with MGA012 (Module B).

- If  $\geq 2$  of these 3 additional participants (i.e.,  $\geq 3$  of the 6 participants enrolled in the cohort) experience a DLT, it will be concluded that the MTD has been exceeded, and 3 participants will be enrolled and treated at the next lower dose level.
- If 1 of these 3 additional participants experiences a drug-related DLT, then another 3 additional participants (for a total of 9 participants in the cohort,  $3 + 3 + 3$ ) will be enrolled and treated at that dose level to further characterize the safety of MGC018 alone (Module A) or in combination with MGA012 (Module B).
- If 0 of the 3 additional participants experiences a DLT, then the dose will be escalated, and 3 participants will be enrolled at the next higher dose level.

If  $\geq 2$  participants out of the first 3 participants treated at a given dose level, or  $\geq 3$  of 6 participants treated at a given dose level, or  $\geq 3$  out of 9 participants treated at a given dose level experience a drug-related DLT, then it will be concluded that the MTD for MGC018 alone (Module A) or in combination with MGA012 (Module B) has been exceeded at that dose level, and all subsequent participants will be treated at the next lower dose level.

If  $\geq 2$  participants out of the first 6 participants treated at a given dose level experience the same drug-related DLT, then the enrollment in that cohort will stop, and it will be concluded that the MTD for MGC018 alone (Module A) or in combination with MGA012 (Module B) has been exceeded and all subsequent participants will be treated at the next lower dose level. In categorizing DLTs, all related MedDRA Preferred Terms will be used to determine whether the same DLT has occurred in a given cohort.

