If  $\geq 2$  participants out of the first 6 participants treated at a given dose level experience a Grade 4 DLT, then the enrollment in that cohort will stop, and it will be concluded that the MTD for MGC018 alone (Module A) or in combination with MGA012 (Module B) has been exceeded and all subsequent participants will be treated at the next lower dose level.

For participants being treated at a dose level subsequently determined to exceed the MTD for a given cohort of the study, the dose of MGC018 alone (Module A) or in combination with MGA012 (Module B) will be reduced to the next lower dose level as summarized in [Table 3](#) and [Table 4](#). Following these rules for dose escalation, the MTD/MAD will be the highest dose administered during the Dose Escalation Phase of the study at which the incidence of DLT is  $< 33\%$ .

Dose escalation to the next dose level is permitted only after the participants enrolled in the current dose cohort have completed the DLT evaluation period and the safety data have been reviewed by the sponsor medical monitor, Independent Safety Monitor, and the investigators participating in the study. Evaluation of safety data from each cohort will include an assessment of the proportion of participants who receive planned doses, and the percentage of participants that require dose reductions or dose discontinuations for toxicity. The sponsor medical monitor, Independent Safety Monitor and investigators will consider all available data from participants both during and beyond the DLT evaluation period when making dose escalation decisions and in the determination of the recommended phase 2 dose to be evaluated in expansion cohorts. In particular, if a Grade 4 febrile neutropenia has been observed, the sponsor will review and evaluate the safety database for other events of any grade febrile neutropenia prior to making a decision to dose escalate.

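### The hematologic DLT list omits anemia while excluding only uncomplicated Grade 3 anemia, so non-hemolytic Grade 4 anemia never counts as a DLT if read literally

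*Protocol*

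**What the plan says.** Protocol Section 4.2 sets up three classes of DLT and no general catch-all: "Dose-limiting toxicities will be defined separately for hematologic, non-hematologic, and hepatic non-hematologic events". Section 4.2.1 gives the hematologic class five items:

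- "Grade 4 neutropenia lasting > 7 days"
- Febrile neutropenia of Grade 3 or higher that exceeds a stated duration, or "febrile neutropenia associated with hemodynamic compromise or objective evidence of infection"
- "Grade 4 thrombocytopenia, irrespective of duration"
- Grade 3 thrombocytopenia with clinically significant bleeding
- Hemolysis of Grade 3 or higher

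The exclusion list under it has two entries: all lymphopenia of Grade 3 or higher, and "Grade 3 anemia that is not associated with other clinically significant complications".

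Section 4.3 turns DLT counts into decisions. With no DLT in the first three participants, "the dose will be escalated, and 3 participants will be enrolled and treated at the next higher dose level". Two or more of 3, three or more of 6, or three or more of 9 means that the MTD is exceeded. A separate rule applies if two or more of the "first 6 participants treated at a given dose level experience a Grade 4 DLT, then the enrollment in that cohort will stop". The MTD/MAD is the highest dose with a DLT incidence below 33%.

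**The concern.** The two lists in Section 4.2.1 point in opposite directions. The inclusion list gives no route for anemia to be a DLT unless it is hemolytic. The exclusion list is written as though anemia were a DLT, with an exception for the milder form. The same cohort can therefore be scored two ways, and the literal score is the less safe one.

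DLTs and the MTD are part of the primary objective, and only DLTs enter the Section 4.3 counts. The Grade 4 stopping rule is affected too, because it needs the event to be a DLT first. So is the rule that stops a cohort for the same DLT in two of the first six.

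Red-cell suppression is plausible for this drug. Protocol Section 2.3.1.1.2 reports "suppressed hematopoiesis (decreased red cell mass and decreased reticulocyte, neutrophil, and platelet counts" with reduced marrow cellularity in monkeys given 20 mg/kg every 2 weeks. In the GLP study, at up to 10 mg/kg every 3 weeks, the red-cell fall was more pronounced from Day 23, but the changes were judged not adverse and they resolved. That timing bears on Module B: its DLT window runs to Day 42 and takes in a second MGC018 dose, whereas Module A's window closed at Day 21. This shows plausibility, not a human rate.

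**Working it through.** **Does any rule make non-hemolytic Grade 4 anemia a DLT?**

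| Place | Scope | Captures it? |
|---|---|---|
| Protocol 4.2.1, five items | Neutropenia, febrile neutropenia, thrombocytopenia (two items), hemolysis | No; hemolysis only if the anemia is hemolytic |
| Protocol 4.2.1, exclusions | Removes uncomplicated Grade 3 anemia | Implies yes, but does not add it |
| Protocol 4.2.2 | Non-hematologic events | No |
| Protocol 4.2.3 | Hepatic events | No |
| Protocol 4.3, Grade 4 rule | Events already classed as DLTs | No |
| Protocol 7.4.3 | Management of anemia: transfuse, discontinue if it persists | Gives no DLT status |
| SAP | Gives the DLT evaluation period but no definition | No |

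Complicated Grade 3 anemia falls into the same gap: it is neither listed nor excluded.

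**Direct consequence.** Suppose 2 of the first 3 participants have drug-related non-hemolytic Grade 4 anemia and no other DLT. The literal score is 0/3: escalate, or no MTD signal at the top planned dose. With anemia counted, the score is 2/3: MTD exceeded.

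**Size under assumed rates.** The plan states no figure to reproduce, and the documents give no anemia rate, so every rate below is an assumption. Let p be the probability that a participant has a countable DLT. For a group of three:

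- G2 = P(2 or more of 3) = 3p²(1−p) + p³
- B1 = P(exactly 1 of 3) = 3p(1−p)²
- G1 = P(1 or more of 3) = 1 − (1−p)³

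The count rules stop at 2 or more in the first three. After 1 of 3, they stop at 2 or more in the second three. After 1 and 1, they stop at any DLT in the third three. Hence

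P(MTD exceeded) = G2 + B1 × (G2 + B1 × G1).

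At p = 0.20: 0.104 + 0.384 × (0.104 + 0.384 × 0.488) = 0.216.

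At p = 0.25: 0.15625 + 0.421875 × (0.15625 + 0.421875 × 0.578125) = 0.325.

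The literal rule uses only the other DLTs. Counting anemia raises p by the share of participants whose only qualifying event is anemia.

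| Other DLTs | Added anemia (points) | Literal | Anemia counted |
|---|---|---|---|
| 10% | 1 | 5.1% | 6.3% |
| 10% | 5 | 5.1% | 12.1% |
| 10% | 10 | 5.1% | 21.6% |
| 20% | 2 | 21.6% | 25.8% |
| 20% | 5 | 21.6% | 32.5% |
| 20% | 10 | 21.6% | 43.9% |
| 20% | 15 | 21.6% | 54.9% |

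The literal column does not move with the anemia rate.

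**Effect of the Grade 4 rule.** The table leaves out the same-DLT and Grade 4 stopping rules. Take all the anemia as Grade 4, and the other DLTs as below Grade 4 and all different. The only extra stopping path is then one anemia in each of the first two groups of three, followed by a clean third group. With anemia rate q and total rate p, this adds [3q(1−p)²]² × (1−p)³.

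- 20% + 5 points: (3 × 0.05 × 0.5625)² × 0.421875 = 0.003, so 32.5% becomes 32.8%.
- 10% + 10 points: (3 × 0.10 × 0.64)² × 0.512 = 0.019, so 21.6% becomes 23.5%.

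**The case against.** The strongest reply is that nothing forces the inference from the exclusion list. Lymphopenia is also excluded without being listed, so the list already contains one entry that changes nothing, and the anemia line might be another. The comparison fails on one point. Lymphopenia is excluded in full from Grade 3 upward, so nothing is left over. The anemia entry is limited by grade and by complication, and those limits have no purpose unless the rest counts.

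Leaving anemia out could be deliberate, because it can be transfused. Section 7.4 requires a hold and a dose reduction on restart after Grade 4 neutropenia or thrombocytopenia. For Grade 4 anemia it asks for transfusion, and for discontinuation only if the anemia persists. This is a possible intent, but the protocol does not state it.

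Several safeguards are real:

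- Under Section 4.3, escalation follows a review of all available data by the medical monitor, the Independent Safety Monitor and the investigators, so 0/3 does not force a higher dose.
- The Module B cohorts planned in Table 4 do not go above the monotherapy MTD of MGC018.
- A drug-related non-hematologic consequence of Grade 3 or higher can be a DLT under Section 4.2.2.

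These limit the harm. None makes the anemia a DLT or corrects the count behind the 33% threshold.

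The evidence of hazard is modest and the rates are assumed. With 10% other DLTs and 1 added point, the change is only from 5.1% to 6.3%. That is a fair limit on the size of the effect, but it does not remove the contradiction.

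**Conclusion.** The concern holds. As written, Section 4.2.1 gives non-hemolytic Grade 4 anemia no route to being a DLT, nor Grade 3 anemia whose complications are not DLTs themselves, while its own exclusion implies that both were meant to count. Nothing elsewhere in the protocol or SAP resolves this.

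The certain part is the scoring conflict: 0/3 against 2/3 for the same cohort, with opposite decisions. The probabilities are illustrative. Over the assumed rates, counting anemia raises the chance of declaring a dose above the MTD by between 1.2 points (5.1% to 6.3%) and 33.3 points (21.6% to 54.9%).

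Module A enrolled 27 participants in escalation and treated 26, and its expansion dose is set. The forward effect is therefore on Module B escalation, planned for up to 27 participants. The definition should be corrected before that starts; the all-data review is a safeguard alongside the count rules, not a substitute for them.

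**What to change.** Before Module B escalation, add two items to the hematologic DLT list in Protocol Section 4.2.1:

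- *Anemia of Grade 4 or higher* (worded so that a fatal case also counts)
- *Grade 3 anemia with clinically significant complications*

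Keep the existing exclusion of uncomplicated Grade 3 anemia. If the sponsor does intend Grade 4 anemia not to count, for example when transfusion corrects it, Section 4.2.1 should say so explicitly.

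The drafting cost is two lines in one section. The operating cost is that a dose will be declared above the MTD more often, so Module B may settle on a lower MGC018 dose.

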#### **4.2.2 Non-hematologic Dose Limiting Toxicity**

Non-hematologic DLT is defined as any  $\geq$  Grade 3 non-hematologic event

- Skin toxicity that meets the definition of Stevens Johnson syndrome (SJS) or toxic epidermal necrolysis (TEN) regardless of duration will be considered a dose limiting toxicity. SJS and TEN are to be reported immediately to the sponsor as an Immediately Reportable Events (IRE) and Adverse Events of Special Interest (AESI) per [Section 12.2.2](#).

The following events will be specifically excluded from the definition of non-hematologic DLT:

- Grade 3 electrolyte abnormality that lasts  $<$  72 hours, is not otherwise associated with clinical complications, and responds to medical intervention
- Grade 3 fever that lasts  $<$  72 hours and is not associated with hemodynamic compromise
- Grade 3 nausea or vomiting that lasts  $<$  72 hours and responds to medical intervention
- Grade 3 or greater amylase and/or lipase elevation that is not associated with clinical or radiographic evidence of pancreatitis requiring hospitalization
- Grade 3 gastrointestinal AEs of diarrhea, constipation, abdominal pain, cramping, dyspepsia, or dysphagia that resolves to  $\leq$  Grade 1 or baseline within 72 hours with maximal supportive care
- Grade 3 fatigue that lasts  $<$  72 hours
- Grade 3 infusion-related reaction (IRR) or cytokine release syndrome (CRS) that lasts  $<$  12 hours and responds to medical intervention
- Grade 3 endocrinopathy that is adequately controlled with hormone supplementation
- Grade 3 skin toxicity that resolves to  $\leq$  Grade 1 or baseline within 72 hours with maximal supportive care
- Grade 3 dry eye or Grade 3 photophobia that lasts  $\leq$  to 72 hours
- Grade 3 inflammatory reaction (e.g., with associated pain, swelling) attributed to a local antitumor response (e.g., inflammatory reaction at sites of metastatic disease, lymph nodes, etc.) that resolves to  $\leq$  Grade 1 or baseline within 5 days

Note: The following Grade 2 non-hematologic AEs may also be considered as DLTs:

- Grade 2 AEs that are prolonged inordinately, based upon the medical judgment of the investigator, and/or lead to permanent discontinuation of study drugs due to participant intolerance
- Any hepatic laboratory abnormalities meeting all 3 Hy's law criteria (described within **Section 4.2.3**)
- Eye pain or reduction in visual acuity that does not respond to topical ophthalmic therapy and does not improve to Grade 1 within 14 days of the initiation of topical ophthalmic therapy, or that requires systemic treatment

#### **4.2.3 Hepatic Non-hematologic Dose Limiting Toxicity**

Hepatic Non-Hematologic DLT will be defined as follows:

- Any elevation of one or more transaminases  $> 8 \times$  the institutional reference laboratory upper limit of normal (ULN) irrespective of duration
- Any Grade 3 elevation of one or more transaminases  $> 5.0 - 8.0 \times$  ULN that does not resolve to Grade 2 (i.e.,  $> 3.0 - 5.0 \times$  ULN) within 7 days and Grade 1 (i.e.,  $>$  ULN -  $3.0 \times$  ULN) within 14 days. In addition, steroids must be tapered to  $\leq 10$  mg of prednisone or equivalent per day, by Day 14. Please see **Section 7.2.2.1** for further management guidelines.
- A Grade 3 elevation of total bilirubin that is  $> 5 \times$  the ULN irrespective of duration.
- Any Grade 3 elevation of total bilirubin  $> 3.0 - 5.0 \times$  ULN that does not resolve to Grade 2 (i.e.,  $> 1.5 - 3.0 \times$  ULN) within 7 days and Grade 1 (i.e.,  $>$  ULN -  $1.5 \times$  ULN) within 14 days. In addition, steroids must be tapered to  $\leq 10$  mg of prednisone or equivalent per day, by Day 14. Please see **Section 7.2.2.2** for further management guidelines.
- Any event meeting the criteria for Hy's law as follows (all 3 features):
  - Aspartate aminotransferase (AST) and/or alanine aminotransferase (ALT)  $> 3 \times$  ULN
  - Concurrent elevation of total bilirubin  $> 2 \times$  ULN without initial evidence of cholestasis
  - No alternative etiology can be identified

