**Cohort Expansion Module B:**

Participants with histologically proven, unresectable, locally advanced or metastatic solid tumors for whom no therapy with demonstrated clinical benefit is available as described below.

- SCCHN that has progressed following treatment with platinum-based chemotherapy for metastatic or recurrent disease, or progression of disease within 6 months of completing prior platinum therapy used as part of neoadjuvant, concurrent chemoradiation, or adjuvant therapy.
  - Participants with upper esophageal or salivary gland tumors will not be considered as SCCHN.
  - Participants who refuse radical resection for recurrent disease are eligible.
- mCRPC that has progressed during or following one prior line of chemotherapy for metastatic disease, and if approved and available, no more than two prior lines of anti-hormonal agent (e.g., abiraterone, enzalutamide) with a PSA value of at least 2 ng/mL and meeting at least one of the following:

- Progression in measurable disease (RECIST v1.1).
- Appearance of 2 or more new bone lesions according to Prostate Cancer Working Group 2 (PCWG2).
- Rising PSA defined as at least two sequential rises in PSA (PSA obtained  $\geq$  1 week apart) over a reference value (the last PSA [PSA  $\geq$  2 ng/mL] measured before the first rise in PSA) (as defined by the PCWG2).

- c. Tumor type TBD at a later date; cancer will be required to have progressed or recurred despite prior standard therapy for that specific tumor.

8. Acceptable laboratory parameters as follows:
  - a. Platelet count  $\geq 100 \times 10^3/\mu\text{L}$  without transfusion within 28 days prior to the initiation of study drug,
  - b. Absolute neutrophil count  $\geq 1.5 \times 10^3/\mu\text{L}$  in the absence of any growth factor support within 21 days prior to the initiation of study drug,
  - c. ALT/AST  $\leq 3.0 \times \text{ULN}$ ; for participants with hepatic metastases, ALT and AST  $\leq 5 \times \text{ULN}$ ,
  - d. Total bilirubin  $\leq 1.5 \times \text{ULN}$ , except participants with Gilbert's syndrome, who may enroll if the conjugated bilirubin is within normal limits,
  - e. Creatinine  $< 2 \text{ mg/dL}$ , or a calculated creatinine clearance (based on the Cockcroft-Gault formula) or measured creatinine clearance  $> 50 \text{ mL/min}$ ,
  - f. Negative urine or serum pregnancy test for women of childbearing potential.
  - g. Albumin  $\geq 3.0 \text{ g/dL}$

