## 7.2.2 Hepatic Toxicity

### 7.2.2.1 Elevations in Transaminases

Management guidelines for participants experiencing hepatic toxicity are as follows:

- Grade 1 elevations - No specific therapy required.
- Grade 2 elevations - For elevations in transaminases 3 to  $5 \times$  ULN, rule out viral and other etiologies. Consider imaging studies such as ultrasound or CT scan and liver biopsy to ascertain etiology of liver dysfunction. Consider starting oral prednisone 60 mg/day divided twice daily and hold study drugs.
  - If improvement to  $\leq$  Grade 1 does not occur within 48 hours with oral steroids, consider IV steroids such as methylprednisolone at 2 mg/kg/day divided twice daily or oral steroids such as prednisone 60 to 120 mg per day, divided twice daily
  - Resume study drugs at the next scheduled dose if no more than one dose of MGC018 alone or in combination with MGA012 was missed.
  - If improvement to  $\leq$  Grade 1 does not occur within 21 days, discontinue study drugs.
- Grade 3 elevations - Hold study drugs.
  - For elevations in transaminases  $> 8 \times$  ULN, permanently discontinue study drugs.
    - Begin immediate IV steroids and,
    - If no response to corticosteroid therapy within 3 to 5 days is observed, consider adding immune suppression therapy with mycophenolate.
    - Monitor liver function tests at least twice weekly (or more frequently as clinically appropriate in the judgment of the investigator) until transaminases have returned to Grade 1 or baseline.
  - For elevations in transaminases  $> 5$  but  $\leq 8 \times$  ULN:
    - Begin immediate IV steroids; suggest methylprednisolone at a dosage of 2 mg/kg/day divided twice daily.
    - Consider additional immune suppression as above for participants who do not respond to corticosteroid therapy within 3 to 5 days.
    - Monitor liver function tests at least twice weekly (or more frequently as clinically appropriate in the judgment of the investigator) until transaminases have returned to Grade 1 or baseline.

- If the elevation does not improve to Grade 2 within 7 days and to Grade 1 within 21 days, discontinue study drugs.
- Resume study drugs administration if following conditions are met:
  - Laboratory elevations improved to  $\leq$  Grade 2 within 7 days and improve to  $\leq$  Grade 1 or baseline within 21 days.
  - Steroids have been tapered to  $\leq$  10 mg per day of prednisone or equivalent.

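### For a transaminase rise of >5 to 8 × ULN, Protocol 7.2.2.1 tells sites both to discontinue and to resume a participant who is back at an admitted baseline above 3.0 × ULN

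*Protocol*

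**What the plan says.** **Entry (Protocol 5.1, criterion 8c).** The usual ALT/AST limit is 3.0 × ULN, but "for participants with hepatic metastases, ALT and AST" may be as high as 5 × ULN. By the bands printed in 4.2.3, Grade 1 ends at 3.0 × ULN and Grade 2 runs from >3.0 to 5.0 × ULN. A participant can therefore be admitted at Grade 2.

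**Management of >5 to 8 × ULN (7.2.2.1).**
- Treatment: "Begin immediate IV steroids; suggest methylprednisolone at a dosage of 2 mg/kg/day divided twice daily".
- Stopping: if the elevation "does not improve to Grade 2 within 7 days and to Grade 1 within 21 days, discontinue study drugs".
- Resuming: allowed at Grade 2 or lower within 7 days and "Grade 1 or baseline within 21 days", with steroids down to 10 mg/day of prednisone or equivalent.

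**Management of Grade 2 (7.2.2.1).** If improvement to "Grade 1 does not occur within 21 days, discontinue study drugs". A separate bullet in this limb allows dosing to resume at the next scheduled dose when no more than one dose was missed.

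**DLT rule (4.2.3).** "Any Grade 3 elevation of one or more transaminases" (>5.0 to 8.0 × ULN) is a DLT unless it falls to Grade 2 within 7 days and to Grade 1 within 14 days. "In addition, steroids must be tapered to" 10 mg/day or less by Day 14. No baseline alternative is given.

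**The concern.** The stopping and resumption bullets cover the same event over the same 21 days, but they use different recovery targets. The difference does not matter for anyone who entered at or below 3.0 × ULN. It does matter for a participant with hepatic metastases admitted above 3.0 × ULN. Full recovery for that person is still Grade 2, so the stopping bullet applies, and the resumption bullet applies as well once steroids are tapered. At stake is whether a fully recovered participant keeps treatment, and whether sites decide alike.

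The same entry limit also interacts with 4.2.3. A related rise that returns completely to an admitted baseline, with steroids tapered on time, still counts as a DLT and so feeds the MTD decision in Module B escalation.

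**Working it through.** **Step 1. Apply the rules to one course.** Peak 6 × ULN, back at baseline by Day 7 and held there, steroids tapered by Day 14, event related to study drug.

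| Baseline (× ULN) | Grade at baseline | DLT (4.2.3) | Discontinue (7.2.2.1) | Resume (7.2.2.1) |
|---|---|---|---|---|
| 0.9, 2.0, 3.0 | ≤1 | no | no | yes |
| 3.1, 4.0, 5.0 | 2 | yes | yes | yes |

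The conflict begins just above 3.0 × ULN. With *or baseline* added to the stopping bullet, the second row gives only *resume*. The first row does not change.

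The bullets could be read so that stopping requires both time limits to be missed. That would remove the conflict, but it would also excuse an elevation that stays at Grade 2 indefinitely, so it is not a credible reading.

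**Step 2. Bilirubin for contrast.** The bilirubin wording follows the same pattern. However, criterion 8d caps entry at 1.5 × ULN, which is the Grade 1 ceiling. Return to baseline therefore always satisfies the Grade 1 step, except in Gilbert's syndrome, "who may enroll if the conjugated bilirubin is within normal limits".

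**Step 3. How many would meet the 7.2.2.1 conflict.** The documents give no frequency. Assume that 5–20% have a baseline above 3.0 × ULN and that 5–10% of those have the event.
- Participants outside Module A escalation, which is already enrolled: 182 − 27 = 155.
- Rate per participant: 0.05 × 0.05 = 0.0025 to 0.20 × 0.10 = 0.02.
- Expected number: 155 × 0.0025 = 0.39 to 155 × 0.02 = 3.1.
- Module A expansion only: 80 × 0.0025 = 0.2 to 80 × 0.02 = 1.6.

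**Step 4. Dose-finding effect of 4.2.3 (Module B escalation only).** Let p be the rate of other DLTs. Let e be the rate of the fully reversed, tapered event among participants without another DLT. The 3+3+3 rules in 4.3 declare the dose above the MTD at ≥2/3, ≥3/6 or ≥3/9. With e = 0:

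P = P(≥2 of 3) + P(1 of 3) × [P(≥2 of 3) + P(1 of 3) × P(≥1 of 3)]

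- p = 0.20: 0.104 + 0.384 × (0.104 + 0.384 × 0.488) = 21.6%.
- p = 0.10: 0.028 + 0.243 × (0.028 + 0.243 × 0.271) = 5.1%.

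For e > 0, replace p by p + (1 − p)e and add the rule that two of the first six with the same DLT stop the cohort. Other DLTs are treated as different terms, and the Grade 4 rule is not modelled.

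| e | p = 0.20 | p = 0.10 |
|---|---|---|
| 0 | 21.6% | 5.1% |
| 0.0025 | 22.0% | 5.3% |
| 0.005 | 22.4% | 5.6% |
| 0.01 | 23.3% | 6.2% |
| 0.02 | 25.0% | 7.4% |

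The increase is 0.3 to 3.4 percentage points. Expected events in 27 participants are at most 27 × 0.0025 = 0.07 to 27 × 0.02 = 0.54.

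If exactly one such event does occur among the first 3 at a dose and p = 0.20:
- Counted: 0.36 + 0.64 × (0.104 + 0.384 × 0.488) = 54.7%.
- Not counted: 0.04 + 0.32 × (0.104 + 0.384 × 0.488) = 13.3%.

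With p = 0.10 the figures are 26.6% and 2.7%. The chance of an event among the first 3 is itself at most about 3e, or 0.75% to 6%.

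**The case against.** **Discretion exists.** Section 4.4.2 requires the medical monitor to be consulted before dosing restarts after a delay, and it permits continuation beyond a 21-day delay when there is clinical benefit. Section 5.4 allows individual continuation with the sponsor's involvement, and 7.2 lets its guidance be adapted to local practice. This stands as mitigation, since a site need not settle the matter alone. None of these provisions says which bullet is the default.

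**The 4.2.3 ceiling may be intended.** It is spelled out as a multiple of ULN. Only 3 of the 11 exclusions in 4.2.2 carry a baseline alternative. Module B adds an anti-PD-1 antibody, for which 7.2 lists autoimmune hepatitis. Strict counting is a legitimate choice, and this largely stands. A reader might infer that 4.2.3 is a plain error that distorts the MTD. The documents do not show that. The large conditional jump in Step 4 depends on a rare event, and participants still tapering steroids at Day 14 are DLTs under either wording. An investigator may also judge the event unlikely to be related (12.1.4).

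**The Grade 2 limb.** A reader might infer that a rise from 3.5 to 4.8 × ULN that returns to 3.5 must end treatment. That is too strong. The limb has its own resumption bullet, and it concerns toxicity, meaning worsening from baseline. Its stopping bullet still lacks a baseline alternative.

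**Conclusion.** The contradiction within 7.2.2.1 for >5 to 8 × ULN is real and follows from the text alone. It affects participants admitted with hepatic metastases at >3.0 to 5.0 × ULN who are at Grade 2 or lower by Day 7 and back at baseline by Day 21 with steroids tapered. It applies in both modules. Deliberate strictness cannot explain it, because the same limb gives opposite instructions.

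Its reach is small: about 0.4 to 3 of up to 155 participants under the assumed rates, which have no source in the documents. A reader might take 155 × 0.05 to 155 × 0.20, about 8 to 31, as the number affected. That counts everyone with such a baseline, not those who also have the event.

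The missing baseline alternative in 4.2.3 is a secondary point. The text does count full recovery to an admitted baseline as a DLT, but whether to relax it is a trade-off. The expected effect on the MTD decision is 0.3 to 3.4 percentage points, in Module B escalation only.

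**What to change.** 1. In 7.2.2.1, >5 to 8 × ULN stopping bullet, change the final condition to *and to Grade 1 or baseline within 21 days*, so that it matches the resumption bullet.
2. In 7.2.2.1, Grade 2 stopping bullet, make the same *or baseline* addition.
3. Before Module B escalation starts, either add *or baseline (whichever is greater)* to the Day 14 step of the transaminase bullet in 4.2.3, or state that the 3.0 × ULN ceiling is intended whatever the baseline.

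Items 1 and 2 cost a few words and change nothing for baselines at or below 3.0 × ULN.

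Item 3 has a price if the rule is relaxed. A related course of 4.9 to 7.9 and back to 4.9 × ULN, with steroids tapered, would no longer count as a DLT, and near 5 × ULN the Day 14 step would add little to the Day 7 step. The >8 × ULN, Hy's law, Day 7 and steroid-taper criteria should stay as they are.
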